## **7.2 *Withdrawal From Study Treatment Due To Adverse Experience***

Subjects withdrawn from receiving additional study drug due to an adverse experience will be followed by the Investigator until the outcome is determined; additional reports will be provided to the Sponsor or regulatory authorities when requested. Every effort will be made to follow the subject for the full study period as per the schedule of Study Visits.

## **7.3 *Management Of Toxicity Related To Study Drug***

Safety will be monitored by assessing vital signs, adverse events, concomitant medications and laboratory and ECG results. ECGs will be conducted in triplicate and vital signs assessed at each Study Visit. During the treatment period, ECGs will be conducted pre and one hour post-dose. Vital signs will be taken pre-dose and following the post-dose ECG.

The most common side effects seen with lonafarnib (the active ingredient of EBP-994) are gastrointestinal (diarrhea, nausea, and vomiting).

There were no serious adverse events (SAEs) observed in the studies conducted in healthy volunteers. The SAEs reported in at least 2% of subjects in the Phase 1 and Phase 2 studies conducted in subjects with solid tumors or hematologic malignancies included fever (6%), diarrhea (6%), dehydration (6%), febrile neutropenia (4%) and sepsis (4%).

As with any anti-viral medication, a possible effect of EBP-994 is viral resistance. Hepatitis D viral load levels will be measured through quantitative PCR at all Study Visits. Viral mutation analysis and resistance phenotyping will be conducted to assess viral resistance to the study medication. The investigator may terminate the subject from the trial if, in his/her opinion, there is an unacceptable increase in HDV viral load. Moreover, the investigator is free to initiate licensed medications at any time point and decrease the dose of EBP-994 if deemed warranted for GI side effects.

During the conduct of the study, safety laboratory values will be assayed within 48 hours of the study visit and the Medical Monitor and Investigator will be informed within 24 hours of assay performance of laboratory abnormalities.

# **8 STATISTICS**

## **8.1 *Blinding***

This is an open-label study; subjects will not be blinded.

## **8.2 *Analysis Populations***

The Safety Population comprises all subjects who are enrolled and receive at least one dose of study drug, and who have at least one post-dosing safety evaluation. All safety endpoints will be analyzed using the Safety Population.

The Per-Protocol Population comprises all subjects who complete at least Study Visit 4, as specified in the protocol. All pharmacodynamic analysis will be conducted using the Per-Protocol Population.

### **8.3 Demographics And Baseline Characteristics**

Demographic and baseline characteristics will be presented descriptively.

### **8.4 Safety**

#### **8.4.1 Adverse Events**

All reported adverse events will be mapped to standard coding terms (MedDRA) and grouped by system organ class and preferred terms. The incidence of adverse events will be tabulated by seriousness, severity, and relationship to study drug. If an adverse event is reported more than once during the study period, the greatest severity and worst-case attribution will be presented in tables. Adverse events will also be listed for individual subjects, along with information regarding onset, duration, severity, and relationship to study drug. Adverse events that lead to withdrawal from the study will be listed and summarized by treatment group separately. Summary tables and listings of serious adverse events will also be generated.

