### Study Design

This study is a phase II, randomized, open-label study up to 48 weeks of treatment with EBP-994 alone, or in combination with Norvir® and/or Pegasys® in subjects chronically infected with HDV genotype 1. The duration of the study for each subject will last approximately 11-55 weeks (up to three week screening period, 4-48 week treatment period and four week safety follow-up period. The duration of the entire study is anticipated to be approximately 45 months (first subject in to last subject out). The investigator is free to initiate licensed medications at any time point and decrease the dose of EBP-994 if deemed warranted for GI side effects.

This study will explore EBP-994 in four groups of treatments:

Group 1: EBP-994 (up to 600 mg daily dose) monotherapy

Group 2: EBP-994 (up to 200 mg daily dose) in combination with Norvir®

Group 3: EBP-994 (up to 600 mg daily dose) in combination with Pegasys®

Group 4: EBP-994 (up to 150 mg daily dose) in combination with Norvir® and Pegasys®

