### **Summary of Dosing Plan/Treatment Plan/Schema**

At the Screening Visit, subjects giving written informed consent will have all required evaluations to determine their eligibility to participate in the study. The outpatient Screening Visit must occur within 21 days of first Study Visit.

Each eligible subject will undergo 8-19 Treatment Study Visits; Screening, Day 1, Day 2, Day 3, Day 7, Day 14, Day 28, then every 4 weeks (total treatment duration depends on assigned treatment group), followed by a Safety Follow-up Visit, 4 weeks post-treatment. Moreover, the investigator is free to initiate licensed medications at any time point and decrease the dose of EBP-994 if deemed warranted for GI side effects.

During the intervals between Study Visits, subjects will be free to carry on their usual activities of daily living. Subjects should be instructed to take the study medication at 24 (QD dosing), 12 (BID dosing) or 8 (TID dosing) hour intervals  $\pm$ 2 hours. Efforts should be made to schedule Study Visits according to the study protocol; however the window for consecutive Study Visits will be  $\pm$ 2 days with the exception of Days 2 and 3 for which a visit window is not allowed.

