## 2 STUDY OBJECTIVES

The primary objectives of the study are to:

- Evaluate the safety and tolerability of 12 weeks of treatment with either a 200 mg po BID dose of EBP-994, or a 300 mg po BID dose of EBP-994, in subjects chronically infected with HDV genotype 1
- Evaluate the pharmacodynamic (PD) activity of a 200 mg po BID dose of EBP-994, vs. a 300 mg po BID dose of EBP-994 on HDV viral load
- Evaluate the pharmacokinetic (PK) profile of a 200 mg po BID dose of EBP-994 vs. a 300 mg po BID dose of EBP-994 in subjects chronically infected with HDV genotype 1
- Evaluate the safety, tolerability, PK, and HDV viral load of a treatment up to 48 weeks with EBP-994 alone, or in combination with Norvir® and/or Pegasys® in subjects chronically infected with HDV

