### **7.1.4 Relationship of Adverse Events to the Study Drug**

The investigator and/or Medical Monitor should record on the CRF whether the event is best described as unrelated, possibly, probably, or definitely related association to the study medications, according to the following definitions.

**Unrelated:** There is evidence that the adverse event definitely has an etiology other than the assigned study drug.

**Possibly Related:** The adverse event has a temporal relationship to study drug administration. However, an alternative etiology may be responsible for the adverse event. Information on drug/product withdrawal may be lacking or unclear.

**Probably Related:** The adverse event has a temporal relationship to study drug administration. The event is unlikely to be related to an alternative etiology. There is a reasonable response on withdrawal (dechallenge). Rechallenge information is not required.

**Related:** The adverse event has a temporal relationship to study drug administration and resolves when the drug is discontinued. An alternative etiology is not apparent. If the subject is rechallenged with the assigned study drug, the adverse event recurs. Rechallenge is not necessarily required.

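### Adverse event incidence is planned over the whole study period with no common time window or exposure adjustment, although treatment lasts 4 to 48 weeks depending on group, so by-group differences can arise from duration alone

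*Combined protocol and SAP*

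**What the plan says.** **AE tables.** Section 8.4.1 (repeated under General in the Protocol Summary) gives the breakdown of the main table: "The incidence of adverse events will be tabulated by seriousness, severity, and relationship to study drug". The counting rule is: "If an adverse event is reported more than once during the study period, the greatest severity and worst-case attribution will be presented in tables". Treatment group is named for one output only: "Adverse events that lead to withdrawal from the study will be listed and summarized by treatment group separately". Tables and listings of serious adverse events (SAEs) are promised without a stated grouping.

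**Denominator.** Section 8.2 says: "All safety endpoints will be analyzed using the Safety Population". That population is all dosed subjects with at least one post-dosing safety evaluation. Length of exposure plays no part in it.

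**Duration.** Study Design in the Protocol Summary gives a "4-48 week treatment period and four week safety follow-up period". The dosing-plan summary says that "total treatment duration depends on assigned treatment group", and Section 3 says much the same. No duration is given for any of Groups 1 to 4.

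**Objectives.** Section 2 has two primary objectives on safety. The first reads in part "Evaluate the safety and tolerability of 12 weeks of treatment with either a 200 mg po BID dose of EBP-994", set against 300 mg BID. The fourth covers safety and tolerability of treatment up to 48 weeks, alone or in combination.

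Section 8 contains no person-time rate, time-to-first-event summary, fixed-window AE table or exposure summary.

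**The concern.** The proportion of subjects with an event rises with time under observation whenever risk continues. Here time under observation is tied by design to the factor being compared. A subject in a 48-week group has far longer to report a first event, or a worse grade of the same event, than a subject in a 4-week group, even if the regimens are equally tolerable.

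Tables built from the wording of Section 8.4.1 could take two forms:
- Pooled over groups, they mix regimens and durations and answer neither primary safety objective.
- Split by group, they mix the effect of regimen with the effect of duration.

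In addition, no table is specified for the 12-week period named in the first objective. Safety and tolerability are primary objectives and the sample size rests on no powered comparison, so these descriptive tables are a main product of the study. AE onset and duration will appear in subject listings. That makes a correction possible but does not correct the summary tables.

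**Working it through.** **1. The plan's own duration figure.** Screening (3 weeks) + treatment + follow-up (4 weeks): 3 + 4 + 4 = 11 and 3 + 48 + 4 = 55 weeks. This reproduces the stated 11–55 weeks per subject.

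**2. Ratio of observation time.** On treatment: 48/4 = 12-fold. AEs are also collected at the four-week post-treatment visit (Section 6.10, Appendix A), so the window from first dose is 8 versus 52 weeks: 52/8 = 6.5-fold. The second ratio matches a count over the study period.

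**3. Constant hazard, identical in every group.** The documents give no event rate, so the weekly first-event hazard h is an assumption, shown over a range. Risk by week w = 1 − exp(−h·w). At h = 2%: 1 − exp(−0.08) = 7.7% at 4 weeks, and 1 − exp(−0.96) = 61.7% at 48 weeks.

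| h per week | 4 wk | 12 wk | 24 wk | 48 wk | 8 wk (4 + 4) | 52 wk (48 + 4) | Ratio, 52 vs 8 wk |
|---|---|---|---|---|---|---|---|
| 0.5% | 2.0% | 5.8% | 11.3% | 21.3% | 3.9% | 22.9% | 5.8 |
| 2% | 7.7% | 21.3% | 38.1% | 61.7% | 14.8% | 64.7% | 4.4 |
| 5% | 18.1% | 45.1% | 69.9% | 90.9% | 33.0% | 92.6% | 2.8 |

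The on-treatment contrast at 2% is 61.7/7.7, about 8-fold. Counting follow-up, as a study-period table would, brings it to about 4.4-fold.

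**4. Front-loaded risk.** Assume a 12-week risk of 20%, so the 12-week cumulative hazard is −ln(0.8) = 0.2231. Place a share f of it in weeks 1–4, so h₁ = 0.2231·f/4. Spread the rest evenly, h₂ = 0.2231·(1 − f)/8, and let h₂ continue afterwards. Risk at 4 weeks = 1 − exp(−4h₁). Risk at 48 weeks = 1 − exp(−4h₁ − 44h₂).

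| Share f in weeks 1–4 | 4 wk on treatment | 48 wk on treatment | Ratio |
|---|---|---|---|
| 50% | 10.6% | 51.6% | 4.9 |
| 80% | 16.3% | 34.6% | 2.1 |
| 100% | 20.0% | 20.0% | 1.0 |

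**5. Does the remedy work?**
- *Constant hazard of 2%:* a first-4-weeks table shows 7.7% in every group. A first-12-weeks table shows 21.3% in every group treated that long. The person-time rate is 2 first events per 100 person-weeks at risk in every group.
- *80% front-loaded:* h₁ = 0.0446 and h₂ = 0.00558. The first-4-weeks table shows 16.3% in every group. The person-time rate is not level. Over 4 weeks it equals h₁, or 4.5 per 100 person-weeks. Over 48 weeks, person-time at risk per subject is 0.163/0.0446 + 0.837 × (1 − exp(−0.245))/0.00558 = 3.7 + 32.6 = 36.3 weeks, so the rate is 0.346/36.3, or 0.95 per 100 person-weeks.

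A rate alone can therefore tilt the comparison the other way, which is why common windows and time to first event are needed beside it.

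**The case against.** **Descriptive pilot.** This is an open-label pilot of up to 75 subjects with no powered comparison, and AE onset and duration are listed by subject. That is a fair reason not to ask for formal inference. It does not justify summary tables that mix regimen with duration when safety is a primary objective.

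**Whole-study incidence serves the 48-week objective.** This stands. A reader might infer that 12 weeks is the only safety objective and that the whole-study table is a mistake. Section 2 does not support that: the fourth primary objective covers up to 48 weeks, so the whole-study table should stay.

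**The text does not say that tables are pooled, or that incidence is a simple percentage.** This also stands. Both would be inferences: the first from silence on grouping, the second from the word incidence together with the worst-grade rule and the Safety Population. Had missing by-group wording been the only gap, it would be a small point of detail. The lack of any common window or exposure adjustment applies however the tables are split.

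**Risk may be early.** A reader might infer that longer-treated groups will necessarily look less safe. The documents do not support this. Section 1.2 describes the known profile as mainly gastrointestinal and dose related but gives no onset timing, and step 4 shows that the effect disappears if all risk falls in weeks 1–4. The point holds as something that can happen in by-group tables.

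**A 12-week table does not suit every group.** Correct. A group treated for 4 weeks cannot fill a 12-week on-treatment window, so that table must be restricted.

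**Conclusion.** The point holds in this form: AE incidence is planned over the whole study period without exposure adjustment or a common window and, apart from AEs leading to withdrawal, is not stated to be by group, while treatment length depends on group. By-group incidence can then differ through duration alone.

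All sizes rest on assumed rates. With a constant 2% per week, the extremes of the planned range give about 15% versus 65% with follow-up counted. With 80% of the 12-week hazard in weeks 1–4, they give about 16% versus 35% on treatment. With all risk in weeks 1–4 there is no distortion.

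The 12-fold exposure ratio and the 8-fold incidence ratio describe weeks on treatment only and should not be read as the expected effect in study-period tables. The difference between any two actual groups cannot be computed, because no group's duration is given. This is a worthwhile, inexpensive improvement to the analysis plan; it does not show that the planned tables will mislead.

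**What to change.** In Section 8.4.1:

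- **(a) Grouping.** State that AE and SAE tables are presented by randomised group and, for the 200 versus 300 mg BID objective, by assigned starting EBP-994 dose. Starting dose is proposed as the classifier because the groups are defined only by maximum daily doses and the investigator may reduce the dose.
- **(b) Whole study.** Keep the whole-study table for the 48-week objective. Add the number of subjects with a first event per person-week at risk, and time to first event.
- **(c) Common windows.** Add a table of events with onset in the first 4 weeks for all groups, and one for the first 12 weeks limited to groups with planned treatment of at least 12 weeks.

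Before the tables are specified, the duration statements must be reconciled and a planned duration given for each group: 4–48 weeks in the Protocol Summary, up to 6 months in Section 1.1, and twenty-four weeks in Section 6.2. The maximum daily doses for Groups 3 and 4 also differ between the Protocol Summary and Section 6.2 and need reconciling before groups are labelled by dose.

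The cost is SAP wording and a few extra tables. AE onset is already recorded on the CRF (Section 7.1.1), and dosing dates are in the subject diary (Section 6.2). No patient procedure changes.

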## 3 STUDY DESIGN

This study is a phase II, randomized, open label study of up to 48 weeks of treatment with EBP-994 alone, or in combination with Norvir® and/or Pegasys® in subjects chronically infected with HDV genotype 1. The investigator is free to initiate licensed medications at any time point and decrease the dose of EBP-994 if deemed warranted for GI side effects. The duration of the study for each subject will be approximately 11-55 weeks (up to three week screening period, up to 48 week treatment period and four week safety follow-up period).

The duration of the entire study is anticipated to be approximately 36 months (first subject in to last subject out). Pharmacokinetic sampling will be done at Day 1 and Day 28 of dosing. PK sampling will be conducted only on subjects who have consented to participate in the PK portion of this study. Participation in PK sampling is optional for each subject.

At the Screening Visit, subjects giving written informed consent will have all required evaluations to determine their eligibility to participate in the study. The outpatient screening visit must occur within 21 days of Study Visit 1.

Each eligible subject will undergo 8-16 Study Visits; Screening, Day 1, Day 2, Day 3, Day 7, Day 14, Day 28, then every 4 weeks (total duration depends on assigned treatment group), followed by a Safety Follow-Up Visit, 4 weeks post-treatment. Study drug will consist of EBP-994 alone or in combination with either Norvir® and/or Pegasys®, depending on which group the subject has been randomized to on the Day 1 visit. Moreover, the investigator is free to initiate licensed medications at any time point and decrease the dose of EBP-994 if deemed warranted for GI side effects.

During the intervals between Study Visits, subjects will be free to carry on their usual activities of daily living. Subjects will be instructed to take their study medication at appropriate dosing intervals. Efforts should be made to schedule Study Visits according to the study protocol; however the window for consecutive Study Visits will be  $\pm 2$  days with the exception of Day 2 and Day 3 for which a visit window is not allowed.

Safety will be monitored by assessing vital signs, adverse events, concomitant medications, laboratory and ECG results. ECGs will be conducted and vital signs assessed at each Study Visit.

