### **7.1.1 Routine Reporting of Adverse Events**

Adverse events, whether or not associated with study drug administration, will be recorded on the Adverse Event Reporting form of the CRF and will be submitted to the sponsor at regularly scheduled intervals.

The information to be entered in the CRF will include:

1. The time of onset of any new adverse event or the worsening of a previously observed adverse event
2. The specific type of reaction in standard medical terminology
3. The duration of the adverse event (start and stop dates)
4. The severity/grade of the adverse event
5. An assessment should be made of the relationship of the adverse event to the study drug, i.e., according to the definitions in Section 7.1.4.
6. Description of action taken in treating the adverse event and/or change in study drug administration or dose

Follow-up assessments should be repeated to document return of any abnormalities to normal, or to document other outcome of the adverse event.

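### The adverse event tables count withdrawals from the study but not stopped or reduced study drug, so they may understate intolerance for a primary objective

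*Combined protocol and SAP*

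**What the plan says.** Tolerability is part of the first primary objective (Section 2 and the Protocol Summary), which sets 200 mg against 300 mg twice daily over 12 weeks. Section 1.2 expects the side effects to be mainly gastrointestinal and dose related.

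Section 8.4.1 plans these adverse event outputs, and the Summary repeats them:

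- Coded incidence: "The incidence of adverse events will be tabulated by seriousness, severity, and relationship to study drug".
- Subject listings, "along with information regarding onset, duration, severity, and relationship to study drug". Action taken with study drug is not among the fields named.
- Serious events: "Summary tables and listings of serious adverse events will also be generated".
- One output defined by consequence: "Adverse events that lead to withdrawal from the study will be listed and summarized by treatment group separately".

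Section 7.2 deals with stopping drug as a state of its own: "Subjects withdrawn from receiving additional study drug due to an adverse experience will be followed by the Investigator until the outcome is determined". It adds: "Every effort will be made to follow the subject for the full study period as per the schedule of Study Visits".

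Section 3 lets the investigator "decrease the dose of EBP-994 if deemed warranted for GI side effects", and the Summary and Section 7.3 say the same. Section 7.1.1, item 6, puts on the CRF for each event: "Description of action taken in treating the adverse event and/or change in study drug administration or dose".

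**The concern.** Tolerability is usually judged on two things: which events occur, and whether subjects can stay on the assigned treatment. Section 8.4.1 covers the first. For the second it offers only departures from the study, whereas the protocol's own responses to intolerance are stopping drug with continued follow-up (Section 7.2) and lowering the EBP-994 dose (Sections 3 and 7.3). Neither enters the withdrawal summary unless the subject also leaves the study.

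At stake is whether the report can say how many subjects sustained each regimen. A dose cut may also limit later events, so incidence alone could flatter a regimen that subjects could not maintain.

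**Working it through.** The plan states no event rate, discontinuation rate, retention rate, power or calculated sample size for this point, so there is no figure to reproduce. The check is a comparison of sections, followed by an illustration.

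**What each planned output would show**

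| What happens to the subject | Incidence, severity and serious event tables | Withdrawal summary |
|---|---|---|
| Adverse event, subject leaves the study | Event shown | Counted |
| Adverse event, drug stopped, subject stays on schedule (7.2) | Event shown, stop not shown | Not counted on a literal reading |
| Adverse event, EBP-994 reduced, subject stays (3, 7.3) | Event shown, reduction not shown | Not counted |

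Severity does not fill the gap, because Section 7.1.3 grades it by effect on daily activity, not by effect on dosing. Section 8 plans no exposure or compliance summary either, although Section 5.4 has compliance measured at each visit.

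**Illustration of size**

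Input from the documents: up to 75 subjects (Section 4) in four groups. Assumed: equal allocation, since no ratio is stated; stop rates of 10% to 30%; retention after stopping of 0%, 50% or 90%.

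Subjects per group: 75 / 4 = 18.75, taken as 19.

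Expected number stopping drug for an adverse event = 19 × stop rate.

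Expected planned count = 19 × stop rate × (1 − share retained). For example, 19 × 0.20 × (1 − 0.90) = 0.38.

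| Assumed stop rate | Expected to stop | Planned count, 0% retained | 50% retained | 90% retained |
|---|---|---|---|---|
| 10% | 1.9 | 1.9 | 0.95 | 0.19 |
| 20% | 3.8 | 3.8 | 1.9 | 0.38 |
| 30% | 5.7 | 5.7 | 2.85 | 0.57 |

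The probability that a group of 19 shows at least one such withdrawal is 1 − (1 − p)^19, with p = stop rate × (1 − share retained). At a 20% stop rate this is 0.986 with none retained (p = 0.20), 0.865 with 50% retained (p = 0.10) and 0.319 with 90% retained (p = 0.02).

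For dose reductions, assume that a further 10% to 30% of subjects have EBP-994 lowered. At a 20% stop rate, the expected number stopping or reducing is 19 × (0.20 + 0.10) = 5.7 to 19 × (0.20 + 0.30) = 9.5 per group. Reductions in subjects who stay add nothing to the planned count.

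**The case against.** The strongest reply is that the gap is narrow. Section 8.4.1 plans a full set of adverse event tables, and diarrhoea bad enough to stop drug would appear in them at its worst severity whatever became of the subject. A reader might infer that study withdrawal is the only planned tolerability count; the documents do not support that. What remains is that no table links an event to its effect on treatment.

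Second, the wording may be loose. Section 4.3 lets the investigator withdraw a subject for an adverse event without separating study from treatment, and Section 7.2 promises effort, not full retention. A sponsor could count subjects who stop drug under the existing summary. This stands as a reason to write that the count may understate intolerance, not that it will. But if the term can be read both ways, two analysts could report different numbers from the same data, and the remedy is the same.

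Third, the study is an open-label pilot with descriptive analysis, and no section ties the choice of regimen to this summary. Section 7.2 applies to every group alike. A reader might infer that the choice of regimen would come out wrong; nothing in the documents shows that a ranking of groups would change.

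Fourth, dose changes are recorded, so no data are lost and the tables could be added at reporting. That is correct. It lowers the severity but leaves the written plan incomplete.

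**Conclusion.** The concern holds as a gap of moderate severity. The only planned summary of adverse events by their effect on treatment is tied to leaving the study; drug discontinuation is a separate state that the protocol tries to keep inside the study; and dose reductions are tabulated nowhere. During treatment, a subject who leaves for an adverse event also stops drug, so the count cannot exceed the number who stop, and it falls as retention improves.

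The size is unknown. With 50% to 90% of such subjects retained, the count captures 50% down to 10% of them; if all of them leave the study, it captures all. This rests on a literal reading of the withdrawal wording, and the counts per group also rest on assumed stop rates and equal allocation. A reader might go further and expect a regimen with many stops to show no withdrawals at all. That requires every subject who stops to be retained, which Section 7.2 seeks but does not guarantee.

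**What to change.** In Section 8.4.1 and the Summary, define the terms and report the number and percentage of subjects, by randomised group, with an adverse event leading to:

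- (a) permanent discontinuation of study drug;
- (b) EBP-994 dose reduction or interruption;
- (c) withdrawal from the study.

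Keep these as separate rows, derive them from the information recorded under Section 7.1.1, item 6, and add action taken to the listing fields. Time to first action is optional. The rules for reducing or stopping drug stay unchanged.

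Add a breakdown by assigned dose where one is recorded. The groups are defined only by maximum daily doses, and the Summary (Group 3 up to 600 mg, Group 4 up to 150 mg) disagrees with Section 6.2 (up to 200 mg for both). Those passages must be reconciled before such a table can be labelled.

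The cost is a few extra tables and possibly some coding, because item 6 asks for a description and the documents do not show a coded field. No new item need be collected. Reported tolerability may look less favourable.
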